#### 7.4.1 Metformin

##### *Treatment:*

Patients will receive metformin ER starting on day -14 for arm 1 and Day -7 for arm 2. The starting dose will be 1000mg PO daily to be administered with evening meal. The tablet should be swallowed whole, and patients will be instructed not to crush, cut or chew medication. On day -7 (or Day 1 for arm 2), patients will increase to 2000mg daily. Metformin will be continued daily with pembrolizumab.

Metformin should continue throughout treatment and even through pembrolizumab delays unless patient is experiencing adverse effects attributed to metformin. Metformin should be taken with food at approximately the same time daily. Patients will be instructed to check their blood sugar if they have any symptoms of hypoglycemia including but not limited to chills/shakiness, cold feeling, lightheadedness, dizziness, etc. Patients will be given a diary to record each dose. They should also be warned that the shell of the ER tablet may be visible in stool and not to be alarmed.

NOTE: Temporarily discontinue metformin in patients undergoing radiologic studies in which intravascular iodinated contrast media are utilized. It is generally recommended that metformin be temporarily discontinued prior to or at the time of intravascular administration of iodinated contrast media (potential for acute alteration in renal function). Continue to withhold metformin for 48 hours after the radiologic study.

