## DOSING DELAYS/DOSE MODIFICATIONS

### 8.1 Metformin ER

Acceptable Dose Reductions for Metformin ER	
Dose Reduction Level	Dose Reduction
1	1000mg
2	500mg

Diarrhea	Management/Next Dose for Metformin ER
≤ Grade 2	No change in dose- can use loperamide to control
Grade 3**	Hold until ≤ Grade 2. Resume at same dose level. Decrease dose to 1000mg daily. Second occurrence can decrease to 500mg daily. Third occurrence, discontinue permanently.
Grade 4	Off protocol therapy
*Patients requiring a delay of >4 weeks should go off protocol therapy.	
**Ensure diarrhea is not due to pembrolizumab (see criteria below).	

Diarrhea	Management/Next Dose for Metformin ER

Recommended management: Loperamide antidiarrheal therapy  Loperamide dosage schedule: 4 mg at first onset, followed by 2 mg with each loose motion until diarrhea-free for 12 hours (maximum dosage: 16 mg/24 hours)  Adjunct anti-diarrheal therapy is permitted and should be recorded when used.
	

Nausea	Management/Next Dose for Metformin ER
≤ Grade 1	No change in dose
Grade 2	Hold until ≤ Grade 1. Resume at same dose level.
Grade 3	Hold* until < Grade 2. Resume at one dose level lower, if indicated.**
Grade 4	Off protocol therapy
*Patients requiring a delay of >4 weeks should go off protocol therapy.	
**Patients requiring > two dose reductions should go off protocol therapy.	
Recommended management: antiemetics.	

Vomiting	Management/Next Dose for Metformin ER
≤ Grade 1	No change in dose
Grade 2	Hold until ≤ Grade 1. Resume at same dose level.
Grade 3	Hold* until < Grade 2. Resume at one dose level lower, if indicated.**
Grade 4	Off protocol therapy
*Patients requiring a delay of >4 weeks should go off protocol therapy.	
**Patients requiring > two dose reductions should go off protocol therapy.	
Recommended management: antiemetics.	

Hypoglycemia	Management/Next Dose for Metformin ER
≤ Grade 1	No change in dose
Grade 2	Hold until ≤ Grade 1. Resume at same dose level.
Grade 3	Hold* until < Grade 2. Resume at one dose level lower, if indicated.**
Grade 4	Off protocol therapy
*Patients requiring a delay of >4 weeks should go off protocol therapy.	
**Patients requiring > two dose reductions should go off protocol therapy.	
Recommended management: antiemetics.	

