### 8.2.1 Management for Immuno-Oncology Agents

Immuno-Oncology (I-O) agents are associated with adverse events that can differ in severity and duration than adverse events caused by other therapeutic classes. Pembrolizumab is considered an immuno-oncology agent in this protocol. Early recognition and management of adverse events associated with immuno-oncology agents may mitigate severe toxicity. Management algorithms have been developed to assist investigators in assessing and managing the following groups of adverse events:

- Gastrointestinal
- Renal
- Pulmonary
- Hepatic
- Endocrinopathies
- Skin
- Neurological.

Investigators should use standard of care algorithms listed in the IB as well as institutional guidelines.

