Stop the pembrolizumab infusion, begin an IV infusion of normal saline, and treat the subject with diphenhydramine 25-50 mg IV (or equivalent) and/or acetaminophen 325 to 1000 mg; remain at bedside and monitor subject until resolution of symptoms. Corticosteroid or bronchodilator therapy may also be administered as appropriate. If the infusion is interrupted, then restart the infusion at 50% of the original infusion rate when symptoms resolve; if no further complications ensue after 30 minutes, the rate may be increased to 100% of the original infusion rate. Monitor subject closely. If symptoms recur then no further pembrolizumab will be administered at that visit. Administer diphenhydramine 25-50 mg IV, and remain at bedside and monitor the subject until resolution of symptoms. The amount of study drug infused must be recorded on the electronic case report form (eCRF). The following prophylactic premedications are recommended for future infusions: diphenhydramine 25-50 mg (or equivalent) and/or acetaminophen 325 to 1000 mg should be administered at least 30 minutes before additional pembrolizumab administrations. If necessary, corticosteroids (recommended dose: up to 25 mg of IV hydrocortisone or equivalent) may be used.

**For Grade 3 or Grade 4 symptoms:** (Severe reaction, Grade 3: prolonged [i.e., not rapidly responsive to symptomatic medication and/or brief interruption of infusion]; recurrence of symptoms following initial improvement; hospitalization indicated for other clinical sequelae)

[e.g., renal impairment, pulmonary infiltrates]). Grade 4: (life threatening; presser or ventilator support indicated).

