Immediately discontinue infusion of pembrolizumab. Begin an IV infusion of normal saline, and treat the subject as follows. Recommend bronchodilators, epinephrine 0.2 to 1 mg of a 1:1,000 solution for subcutaneous administration or 0.1 to 0.25 mg of a 1:10,000 solution injected slowly for IV administration, and/or diphenhydramine 50 mg IV with methylprednisolone 100 mg IV (or equivalent), as needed. Subject should be monitored until the investigator is comfortable that the symptoms will not recur. pembrolizumab will be permanently discontinued. Investigators should follow their institutional guidelines for the treatment of anaphylaxis. Remain at bedside and monitor subject until recovery from symptoms. In the case of late-occurring hypersensitivity symptoms (e.g., appearance of a localized or generalized pruritus within 1 week after treatment), symptomatic treatment may be given (e.g., oral antihistamine, or corticosteroids).

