### 9.1 Investigational Agent

#### 9.1.1 Metformin

Availability: Commercial Metformin ER will be used as supply and will be obtained from the site investigational drug pharmacy.

Agent Ordering and Agent Accountability: Metformin will be requested from the investigational drug pharmacy at each participating institution.

Agent Inventory Records: The investigator, or a responsible party designated by the investigator, must maintain a careful record of the receipt, dispensing and final disposition of all agents received from IDS.

Investigator Brochure Availability: Metformin ER is a commercial product. Therefore, no IB will be provided.

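### The hypoglycemia table for metformin ER recommends antiemetics, which do not treat low blood glucose

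*Combined protocol and SAP*

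**What the plan says.** Section 8.1 sets out, event by event, what to do with metformin ER when a toxicity occurs. Four events have a table: diarrhea, nausea, vomiting and hypoglycemia.

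- The diarrhea table carries its own treatment line, "Recommended management: Loperamide antidiarrheal therapy", followed by a loperamide dosing schedule.
- The nausea, vomiting and hypoglycemia tables each end with "Recommended management: antiemetics".
- For hypoglycemia, the rows above that line leave the dose unchanged at grade 1 or below, hold metformin and resume at the same dose for grade 2, hold and resume one level lower if indicated for grade 3, and stop protocol therapy for grade 4.

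Section 7.4.1 (Metformin) deals with recognition: "Patients will be instructed to check their blood sugar if they have any symptoms of hypoglycemia". It says nothing about what to do if the reading is low. Section 3.2.2 mentions hypoglycemia twice, once to say that metformin does not usually cause it and once to report that none was seen in the earlier phase I study.

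**The concern.** Antiemetics treat nausea and vomiting and do nothing for low blood glucose, so the line cannot be right under the hypoglycemia heading. Section 8 is the operative guidance: section 7.4 sends investigators there for dose modifications, and section 8.2 tells them to follow the metformin guidance when they attribute an event to metformin. A site that looks up a hypoglycemic patient would find workable rules on holding the drug, but a recommended treatment that does not address the problem.

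What is at stake is the accuracy of a safety instruction. Nothing statistical depends on it.

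**Working it through.** No arithmetic applies beyond counting. The check sets the tables side by side and then looks for any other text that supplies a treatment.

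**Step 1: compare the section 8.1 tables.**

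| Event | Grade rows | Footnotes | Recommended management | Fits the event? |
|---|---|---|---|---|
| Diarrhea | its own | its own | loperamide | yes |
| Nausea | reference | reference | antiemetics | yes |
| Vomiting | 4 of 4 identical to nausea | 2 of 2 identical | antiemetics | yes |
| Hypoglycemia | 4 of 4 identical to nausea | 2 of 2 identical | antiemetics | no |

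The antiemetics line occurs 3 times and is right in 2. The nausea, vomiting and hypoglycemia tables differ only in their heading, which makes copying the likely cause. That is an inference, and the error does not depend on it. The diarrhea table shows what was intended: a treatment specific to the event.

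**Step 2: look for a treatment elsewhere.** Hypoglycemia comes up in four places.

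| Place | What it says | Names a treatment other than antiemetics? |
|---|---|---|
| 3.2.2, general background | not usual on metformin | no |
| 3.2.2, phase I experience | none observed | no |
| 7.4.1 | symptoms prompt a blood sugar check | no |
| 8.1, hypoglycemia table | hold, reduce or stop metformin; antiemetics | no |

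The count is 0 of 4.

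**Step 3: check text that might cover it indirectly.**

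- The clause in section 8.1 on intolerable side effects below grade 3 gives an open-ended list of supportive drugs. It names loperamide, omeprazole and anti-emetics, and nothing that raises glucose.
- Section 8.2.5 names corticosteroids and epinephrine, which can raise glucose, but only for infusion reactions to pembrolizumab.
- Section 8.2.1 does defer to outside guidance, "Investigators should use standard of care algorithms listed in the IB as well as institutional guidelines", but for immuno-oncology events.
- Section 9.1.1 rules out that route for metformin: "Metformin ER is a commercial product. Therefore, no IB will be provided". Sections 7.4 and 9 point to the metformin package insert for adverse events and risks. The insert is not part of the protocol, so its content is not judged here.

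Nothing in the protocol text overrides or completes the line.

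**The case against.** The strongest reply is that the line will not mislead anyone. Section 11.6 has a qualified physician evaluate every adverse event, and such a physician would not give an antiemetic for low glucose. The line is only a recommendation, and section 7.8 allows other medication that the investigator considers medically necessary. Glucose is in the chemistry panel (section 7.5.7, Table 1), and the study calendar schedules chemistry at screening, on the lead-in days and on day 1 of each cycle, so detection does not rest on self-checks alone. Sites also have access to the metformin package insert. Holding metformin, which the table does require from grade 2 upward, is itself part of management.

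All of this stands as a limit on the consequence. None of it makes the line correct. Holding the suspected drug is dose management and does not treat a glucose that is already low. The package insert may or may not cover treatment, but the protocol table would still say something different from what is needed.

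The reassurance from phase I should not be pressed far. No hypoglycemia was seen at doses up to 3000 mg daily, against 2000 mg here, but metformin was given with cisplatin and radiation, many patients stopped it, most often at the highest dose, and the number treated is not given. No upper limit on the event rate can be derived from it.

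**Conclusion.** The line is wrong as written. It is a drafting error confined to the last line of one of the four event tables in section 8.1. The rest of the hypoglycemia table applies to the event and is not in question.

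The weight is minor, at the bottom of that range: no endpoint, dose-limiting toxicity definition, stopping rule, sample size or analysis changes, and the chance of harm is very low. The conclusion rests on the ordinary clinical fact that antiemetics do not correct low glucose. The statement that no other treatment is named covers the protocol text available for review, which lacked a few front pages, and does not extend to the package insert.

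**What to change.** Replace only the last line of the hypoglycemia table. Leave its rows and footnotes, and the nausea and vomiting tables, as they are. A sufficient wording is:

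*Recommended management: check blood glucose and treat per institutional standard.*

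This uses a check that section 7.4.1 already asks of symptomatic patients, and follows the deferral to institutional guidelines that section 8.2.1 makes for pembrolizumab. If the sponsor's clinicians want more detail, they could name oral carbohydrate, with IV dextrose or glucagon when the patient cannot swallow safely. Those agents are a suggestion and do not appear in the protocol. The non-oral option would matter for dysphagia that develops on study, which section 10.2 anticipates, since exclusion criterion 14 already keeps out patients who cannot swallow pills at entry. Deleting the line would also remove the error, but would leave this table without the treatment guidance that the other three have.

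The cost is one line in the next amendment. The minimum wording adds no scheduled procedure and no data collection.

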Tumors can express tumor-specific antigens as a result of mutational burden, and ongoing immune surveillance is believed to control the development of many tumors. Tumor progression may depend on the acquisition of mechanisms that permit them to evade an effective immune response. One such mechanism of evasion may be the expression of ligands, which engage inhibitory receptor(s) on anti-tumor T-cells of many tumors. PD-L1 expression has been found on a number of tumors and may be a mechanism by which tumors can directly engage PD-1 to evade an effective anti-tumor immune response. Expression of IFN- $\gamma$  by activated T cells is known to induce PD-L1 expression in tumors. PD-1 engagement on T-cells by PD-L1-positive APC or PD-L1-positive tumor cells in the tumor microenvironment may limit effective immune responses. Conversely, PD-L1 expression may be a positive prognostic factor as it may indicate infiltration of tumor-specific T cells that secrete IFN- $\gamma$ , which up regulates PD-L1 expression. Consistent with this hypothesis is the co-localization of lymphoid cell infiltrates and PD-L1 staining observed in human melanoma lesions.

Pembrolizumab is a potent and highly selective humanized monoclonal antibody (mAb) of the IgG4/kappa isotype designed to directly block the interaction between PD-1 and its ligands, PD-L1 and PD-L2. The PD-1 cell surface membrane receptor is a negative regulatory molecule expressed by activated T and B-lymphocytes as well as NK cells. Pembrolizumab has been approved in the metastatic setting for lung cancer, renal cell cancer, melanoma, and metastatic HNSCC among others as mentioned above. Several studies are now ongoing to study PD-1 inhibitor combinations in the upfront and adjuvant setting. The safety profile of pembrolizumab is well-established. Immunotherapy is unique in that auto-immune type of adverse events (AEs) can occur and must be managed appropriately most often with steroids. In keynote 48, the most common AEs in the pembrolizumab group were fatigue, rash, diarrhea and nausea with 6.3%

Grade 3 or higher immune related AEs and 54.7% Grade 3 or higher AEs overall, which was significantly lower than the extreme regimen (83.3%). Here, we propose to use the FDA approved every 3 week schedule of 200mg flat dose or the most recently FDA approved dose of 400mg every 6 weeks (<https://www.fda.gov/drugs/drug-approvals-and-databases/fda-approves-new-dosing-regimen-pembrolizumab>).

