## 7.4 Agent Administration

Treatment will be administered on an outpatient basis. Reported adverse events and potential risks are described in the Investigators Brochure for Pembrolizumab and the package insert for Metformin. Appropriate dose modifications are described in Section 8. No investigational or commercial agents or therapies other than those described below may be administered with the intent to treat the patient's malignancy.

Regimen Description					
Agent	Premedications; Precautions	Dose	Route	Schedule	Cycle Length
Pembrolizumab	No premedications; No steroids	200mg or 400mg	IV over 30 minutes	Days 1, week 1 (for 400mg	21 days (3 weeks)

				dose, therapy only given q6 weeks and on odd cycles)	
Metformin*	No premedications	1000mg for first 7 days followed by 2000mg daily	Oral	Daily	Continuous**

* The patient will be requested to maintain a medication diary of each dose of medication. The medication diary will be returned to research staff at the end of each course.
 
** Metformin will be escalated per schema and then given continuously throughout pembrolizumab cycles.
					

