**Lactic acidosis:** In a very small proportion of patients, lactic acidosis defined as lactate levels >5 can occur with metformin especially those with renal impairment. Due to the seriousness of this event, metformin should be permanently discontinued.

**Renal dysfunction:** Although metformin does not cause renal dysfunction, the clearance of metformin and therefore risk of lactic acidosis increases in renal dysfunction. Therefore, metformin dose should be decreased by 50% if eGFR is 30 to 45ml/min and held if eGFR is <30ml/min. Metformin may be restarted at full dose (using dose escalation as provided) once kidney function improves above these parameters.

**Vitamin B12 deficiency:** Metformin does not need to be held for this indication as long as B12 is replaced.

**Other Toxicities:** For any other grade 3-4 adverse events (besides those mentioned above), hold metformin until toxicities have recovered to grade 1 or less.

**Dose Reduction for Intolerability:** If patients have side effects that are considered intolerable to patient but are less than grade 3, support patients with supportive medications (loperamide, omeprazole, anti-emetics, etc.) and try alteration of their dosing schedule by reducing by 1 dose level at a time until toxicity is  $\leq$  grade 1 for 1 week. Then attempt to re-escalate to protocol dose. Every attempt should be made to keep metformin dose at protocol dose but if unable to achieve the assigned dose, then metformin should be maintained at highest dose tolerated for remainder of treatment.

NOTE: Temporarily discontinue metformin in patients undergoing radiologic studies in which intravascular iodinated contrast media are utilized. It is generally recommended that metformin be temporarily discontinued prior to or at the time of intravascular administration of iodinated contrast media (potential for acute alteration in renal function). Continue to withhold metformin for 48 hours after the radiologic study.

NOTE: If metformin is held at any time for any reason for longer than 1 week, upon restarting the drug, it must be dose escalated again slowly with 1000mg daily for 1 week prior to escalation to 2000mg daily.

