## 8.2 Pembrolizumab

Adverse events (both non-serious and serious) associated with pembrolizumab exposure may represent an immunologic etiology. These adverse events may occur shortly after the first dose or several months after the last dose of treatment. Pembrolizumab must be withheld for drug-related toxicities and severe or life-threatening AEs as per below. It will be up to investigator to determine if each AE is attributed to metformin (and follow guidelines above) or pembrolizumab to follow guidelines below.

Pembrolizumab administration should be delayed for the following:

- Any Grade  $\geq 2$  non-skin, drug-related adverse event, with the following exceptions:
  - Grade 2 drug-related fatigue or laboratory abnormalities do not require a treatment delay
- Any Grade 3 skin, drug-related adverse event
- Any Grade 3 drug-related laboratory abnormality, with the following exceptions:
  - Grade 3 amylase or lipase abnormalities that are not associated with symptoms or clinical manifestations of pancreatitis do not require a dose delay.
  - If a subject has a baseline AST, ALT, or total bilirubin that is within normal limits, delay dosing for drug-related Grade  $\geq 2$  toxicity

- If a subject has baseline AST, ALT, or total bilirubin within the Grade 1 toxicity range, delay dosing for drug-related Grade  $\geq 3$  toxicity
- Any adverse event, laboratory abnormality, or intercurrent illness, which, in the judgment of the investigator, warrants delaying the dose of study medication

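### For a Grade 3-4 adverse event attributed to neither drug, Section 8.1 holds metformin and Section 7.4.1 continues it; Section 8.2 does not settle the case

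*Combined protocol and SAP*

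**What the plan says.** Three places govern what happens to metformin when a patient has a severe adverse event.

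- Section 7.4.1 (Metformin, Treatment): "Metformin should continue throughout treatment and even through pembrolizumab delays unless patient is experiencing adverse effects attributed to metformin". Interruption for an adverse effect depends on attribution to metformin.
- Section 8.1 (Metformin ER, Other Toxicities): "For any other grade 3-4 adverse events (besides those mentioned above), hold metformin until toxicities have recovered to grade 1 or less". The trigger is grade alone.
- Section 8.2 (Pembrolizumab, opening paragraph): "It will be up to investigator to determine if each AE is attributed to metformin (and follow guidelines above) or pembrolizumab to follow guidelines below". Each event is sent to one set of guidelines or the other.

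Section 7.4 also tells the reader that "Appropriate dose modifications are described in Section 8", without saying which text prevails if they differ. Section 8.1 closes with a note on restarting: "If metformin is held at any time for any reason for longer than 1 week, upon restarting the drug, it must be dose escalated" again, with a week at 1000 mg before the return to 2000 mg.

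**The concern.** Section 11.1 defines an adverse event without requiring a causal link to treatment, and its causality scale includes unrelated and unlikely. By the protocol's own definition, then, the 8.1 sentence covers severe events caused by the cancer or by something else. For such an event a site cannot follow both 8.1 and 7.4.1.

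Metformin is the agent added to pembrolizumab, and Section 10.2 treats 6 responses in 19 evaluable patients as reason to pursue the combination. If sites resolve the conflict differently, patients with the same kind of event will have different metformin exposure. A low response rate would then be harder to read: the combination may be inactive, or metformin may have been interrupted. The correlative samples drawn while metformin is being taken (Cycle 1 Day 1 in Arm 1, Cycle 2 Day 1 in both arms) are open to the same ambiguity.

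**Working it through.** The plan states no figure on this point, so there is none to reproduce. The check is a comparison of the three texts by attribution case, followed by two scale calculations.

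**Step 1. The instructions side by side**, for a Grade 3-4 event with no specific rule of its own in 8.1:

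| Attributed to | 7.4.1 | 8.1 Other Toxicities, as worded | 8.2 routing | Result |
|---|---|---|---|---|
| Metformin only | continuation rule does not apply | hold | to 8.1 | consistent |
| Pembrolizumab only | continue | hold | to 8.2, so 8.1 is not entered | settled by 8.2, in line with 7.4.1 |
| Both | continuation rule does not apply | hold | not expressly assigned (worded as one or the other) | routing gap |
| Neither | continue | hold | none | opposite instructions |

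**Step 2. Can an attribution condition be read into 8.1?** Not safely.

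- Where the authors wanted one, they wrote it. The Grade 3 diarrhea footnote in 8.1 reads "Ensure diarrhea is not due to pembrolizumab (see criteria below", and 8.2 repeatedly limits its rules to drug-related events.
- Section 8.1 is not confined to events caused by metformin. Its renal rule reduces or holds metformin while stating that metformin does not cause renal dysfunction.

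**Step 3. Length of an interruption.** Inputs: the restart note in 8.1 (a hold over 1 week adds 1 week at 1000 mg) and the 21-day cycle in 7.4.

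Days below 2000 mg = days held + 7. For the shortest whole-day hold that triggers the note: 8 + 7 = 15 days, against a 21-day cycle.

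**Step 4. A ceiling on the number of patients.** Inputs: 54.7% of the pembrolizumab group in the first-line trial described in Section 3.2.1 had a Grade 3 or higher event ("Grade 3 or higher immune related AEs and 54.7% Grade 3 or higher AEs overall"); Section 10.2 plans 25 enrolled and 19 evaluable.

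- Enrolled: 0.547 × 25 = 13.7, about 14.
- Evaluable: 0.547 × 19 = 10.4, about 10.

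These count patients with any Grade 3 or higher event. They include Grade 5 events, events with their own rule in 8.1 (diarrhea, nausea, vomiting, hypoglycemia), events attributed to pembrolizumab, and events that might here be attributed to metformin. The contested subset is what remains after all of these are removed, and the documents give no rate for it. Nor do they give the length of such holds.

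**The case against.** The strongest reply is that Section 8 already has a structure. The routing sentence in 8.2 makes attribution to metformin the way into 8.1, which agrees with 7.4.1, and the diarrhea footnote applies the same logic. For events attributed to pembrolizumab alone this stands. A reader might infer from 8.1 and 7.4.1 read alone that a pembrolizumab immune event also draws opposite metformin instructions. The documents do not support that: 8.2 sends such an event to its own guidelines. The 6.3% immune-event rate in Section 3.2.1 (0.063 × 25 = 1.6 patients) is therefore not a measure of the conflict.

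The reply does not reach events attributed to neither drug, because the routing sentence names only two destinations. It also sits in the pembrolizumab section, where someone looking up a metformin hold in 8.1 may not see it.

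It is also fair to say that the statistical consequence is limited. Evaluability for response in Section 13.1.1 has no metformin-intensity condition. Section 7.3.5 requires documented consultation with the coordinating investigator for interruptions over 4 weeks. Sections 7.4 and 7.5.1 already require a dose diary, causality and the action taken with trial treatment. All of this stands, and it means no new data collection is needed. None of it tells a site which instruction to follow.

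**Conclusion.** The contradiction is real but narrow. For Grade 3-4 events attributed to neither drug and without their own rule in 8.1, Sections 8.1 and 7.4.1 cannot both be followed. Events attributed to both drugs are left without an express route. Events attributed to one drug alone are settled. This is an error in the instructions as written, not merely missing detail.

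The size cannot be estimated from the documents. A reader might take 54.7%, or about 14 of 25 patients, as the difference between the two readings. It is only a loose ceiling, for the reasons in the working. Even as a ceiling it assumes that the rate carries over from a first-line trial of pembrolizumab to patients who may have had up to three prior lines (Section 4.1) and who also take metformin. It counts patients over their whole exposure, not days off metformin before response is assessed.

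No sample size, success threshold or error rate changes. The effect is on metformin dose intensity, lengthened by the re-escalation week after any hold over 1 week, and so on interpretation of the response rate and correlative samples. No view is taken on which clinical instruction is right.

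**What to change.** Reconcile Section 7.4.1, Other Toxicities in Section 8.1 and the opening of Section 8.2, so that one instruction covers each attribution case: metformin, pembrolizumab, both, neither. State the scope of the 8.1 sentence in 8.1 itself. The sponsor's clinicians decide what each instruction is.

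Metformin exposure can be summarised beside the response rate, using the medication diary and the causality and action-taken data already collected.

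The cost is a short wording amendment across three sections and one descriptive summary: no extra patients, procedures or data items.

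### The metformin restart rule in section 8.1, read as written, raises a dose-reduced patient to 2000 mg after a hold of more than 1 week, where the Grade 2 tables keep the reduced dose

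*Combined protocol and SAP*

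**What the plan says.** Section 8.1 allows two reduced metformin levels, 1000 mg and 500 mg. Each toxicity table has a column headed "Management/Next Dose for Metformin ER". In the nausea, vomiting and hypoglycemia tables, the Grade 2 row holds the drug until the event is at or below "Grade 1. Resume at same dose level". That row gives no discretion and no time limit. The Grade 3 row of the same tables reads "Resume at one dose level lower, if indicated", and a footnote takes patients who need more than two reductions off protocol therapy.

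The text after the tables has a paragraph on side effects below Grade 3 that the patient cannot tolerate. It reduces the dose one level at a time, says "Then attempt to re-escalate to protocol dose", and ends: "if unable to achieve the assigned dose, then metformin should be maintained at highest dose tolerated for remainder of treatment".

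The section's closing NOTE covers metformin that is "held at any time for any reason for longer than 1 week, upon restarting the drug, it must be dose escalated again slowly". The schedule it then sets is a first week at half the full dose, followed by the full 2000 mg. It names no other destination dose, does not mention patients on a reduced level, and does not say how it relates to the tables.

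**The concern.** Take a patient already reduced to 500 mg or 1000 mg who then has Grade 2 nausea, vomiting or hypoglycemia that takes more than a week to settle. The table returns that patient to the reduced dose. The NOTE, which is mandatory and applies to any hold for any reason, takes the patient to 2000 mg. A slower recovery from the same event therefore leads to a higher dose, which is the reverse of what toxicity management intends.

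A site that follows the NOTE re-exposes the patient to a dose already cut for toxicity, with no fresh decision to re-escalate. There is also a knock-on effect. A patient who reached 500 mg through the listed levels has normally used two reductions. If the NOTE returns that patient to 2000 mg and Grade 3 nausea, vomiting or hypoglycemia recurs, another reduction would be the third, and the footnote would end protocol therapy. The protocol provides for participating sub-sites (sections 5.1 and 14.1), so different readings could give the same patient daily doses that differ by up to 4 times.

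**Working it through.** The plan gives no figure to reproduce here. The check is to follow each instruction for each possible dose before the hold, and then to look for text that reconciles them.

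**Inputs, all from section 8.1**
- Reduced levels: 1000 mg and 500 mg daily; full dose 2000 mg daily.
- Grade 2 nausea, vomiting or hypoglycemia: resume at the dose held before.
- NOTE, for holds longer than 1 week: 1000 mg daily for 7 days, then 2000 mg daily.
- Comparison window: the first 21 days after restart, which is one cycle (section 7.4).

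**Formulas**
- NOTE total = 7 × 1000 + 14 × 2000 = 35,000 mg, whatever the dose before the hold.
- Table total = 21 × dose before the hold.

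| Dose before hold | Table, 21 days | NOTE, 21 days | Ratio of totals | Daily ratio, days 1–7 | Daily ratio, from day 8 |
|---|---|---|---|---|---|
| 500 mg | 21 × 500 = 10,500 mg | 35,000 mg | 35,000/10,500 = 3.33 | 1000/500 = 2 | 2000/500 = 4 |
| 1000 mg | 21 × 1000 = 21,000 mg | 35,000 mg | 35,000/21,000 = 1.67 | 1000/1000 = 1 | 2000/1000 = 2 |
| 2000 mg | 21 × 2000 = 42,000 mg | 35,000 mg | 0.83 | 0.5 | 1 |

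The excess is 35,000 − 10,500 = 24,500 mg for the 500 mg patient and 35,000 − 21,000 = 14,000 mg for the 1000 mg patient. For a 2000 mg patient the NOTE adds a cautious titration week and ends at the same dose, so there is no concern there.

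**Threshold.** A hold of exactly 7 days is not longer than 1 week, so the table applies and a 500 mg patient is scheduled for 10,500 mg. At 8 days the NOTE applies and the schedule is 35,000 mg. One more day off drug adds 24,500 mg over the next 21 days.

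**Search for reconciling text**
- No sentence in section 8.1 ranks the NOTE against the tables, and the dosing text in sections 7.4 and 7.4.1 does not either.
- The intolerability paragraph sets a ceiling, but only for effects below Grade 3, and the NOTE does not refer to it. Reductions made after Grade 3 nausea, vomiting or hypoglycemia fall outside it.
- The renal paragraph has its own rule for returning to full dose, so renal holds are not part of this point.
- The Grade 3 nausea, vomiting and hypoglycemia rows conflict with the NOTE only when a reduction is judged indicated.
- The Grade 3 diarrhea cell says both to resume the same dose and "Decrease dose to 1000mg daily. Second occurrence can decrease to 500mg daily". It is unclear in itself and is not relied on.
- The 4-week limit is marked on the Grade 3 rows, not the Grade 2 rows, and section 7.3.5 asks only for consultation after 4 weeks. No upper bound on a Grade 2 hold is therefore assumed.

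**The case against.** The strongest reply is that the NOTE is about pace, not destination. Its wording echoes the starting titration in sections 7.4 and 7.4.1, so it was probably written for patients on full dose. The rest of section 8.1 treats reductions as lasting: it numbers the levels, limits the number of reductions, and heads the tables as giving the next dose. Read as a whole, the section points to titration up to the assigned level, and a site could reasonably let the table govern. That reading is fair, but the text does not secure it. It also fails for the 500 mg patient, whose first dose under the NOTE is already twice the assigned dose.

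The second reply is that the case is narrow. It needs an earlier reduction, a later Grade 2 event of a listed type, and a hold of more than a week, in a trial of 25 patients. This stands: the documents give no frequency for such holds, and it may be zero.

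The third reply is that the totals are upper bounds, because a recurrence would trigger another hold or reduction before 14 days at 2000 mg had passed. This also stands. The figures are scheduled dose without further interruption.

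Finally, the harm is bounded. The study dose is 2000 mg, re-challenge is already policy for effects below Grade 3, and a recurrence meets the same hold, reduce and stop rules. These points limit the size of the problem; they do not make the two instructions compatible.

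**Conclusion.** The concern holds. Followed as written, the NOTE overrides an existing toxicity reduction after any hold longer than 1 week. It contradicts the Grade 2 nausea, vomiting and hypoglycemia rows for patients on 500 mg or 1000 mg. The scheduled daily dose rises to 4 times or 2 times the table dose from day 8.

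This rests on a literal reading of the NOTE and, for the 21-day totals, on uninterrupted dosing after restart. How many patients would be affected cannot be judged from the documents. It is a patient-safety and site-consistency correction; no endpoint or sample-size figure changes.

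**What to change.** Replace the NOTE with text such as: *If metformin is held for longer than 1 week, restart at 1000 mg daily for 1 week (or at 500 mg if that is the currently assigned dose), then escalate to, but not above, the dose level currently assigned under section 8.1. Return to full dose after renal recovery, and the re-escalation attempt for intolerability below Grade 3, remain as stated in those paragraphs.*

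Check over 21 days:
- Assigned 500 mg: 21 × 500 = 10,500 mg, equal to the table.
- Assigned 1000 mg: 7 × 1000 + 14 × 1000 = 21,000 mg, equal to the table.
- Assigned 2000 mg: 7 × 1000 + 14 × 2000 = 35,000 mg, unchanged from the present NOTE.

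The cap needs a defined assigned level, so the Grade 3 diarrhea cell should be clarified in the same amendment. The NOTE itself costs one amended sentence and a memo to sites, with no added visits, patients or data items.
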